17.3. Audits and Inspections

Authorized representatives of Celularity, a regulatory authority, an IRB/EC may visit the site to perform audits or inspections, including source data verification. The purpose of a Celularity audit or inspection is to systematically and independently examine all study-related activities and documents to determine whether these activities were conducted, and data were recorded, analyzed, and accurately reported according to the protocol, Good Clinical Practice guidelines of the ICH, and any applicable regulatory requirements. The investigator should contact Celularity immediately if contacted by a regulatory agency about an inspection.

The Investigator and/or Study site is required to permit direct access to the facilities where the study took place, source documents, eCRFs and applicable supporting records of study subject participation for audits and inspections by IRB/ECs, regulator authorities (e.g., FDA, European Medicines Agency (EMA), Medicines and Healthcare products Regulatory Agency (MHRA), Health Canada (HC) and Celularity authorized representatives. The Investigator should make every effort to be available for the audits and/or inspections. If the Investigator is contacted by any regulatory agency regarding an inspection, he/she should contact Celularity immediately.

17.4. Institutional Review Board (IRB)

The Investigator must obtain IRB approval for the investigation. Initial IRB approval, and all materials approved by the IRB for this study including the informed consent form and recruitment materials must be maintained by the Investigator and made available for inspection.

The Investigator must keep a record of all communication with the IRB/EC and, if applicable, between a Coordinating Investigator and the IRB/EC. This statement also applies to any communication between the Investigator (or Coordinating Investigator, if applicable) and regulatory authorities. All materials approved by the IRB/EC for this study including the patient consent form and recruitment materials must be maintained by the Investigator and made available for to the monitor.

18. PUBLICATION POLICY

With exception to the information provided by Celularity on the public registry websites and/or Celularity approved recruitment material, any information regarding this clinical study is considered confidential and/or proprietary and is not to be used in any publications, press releases or other public disclosure without the written approval from an authorized representative of Celularity. Celularity protocol-related information proposed for use in a publication must be submitted to Celularity for review and written approval prior to publication, as agreed and described in the Clinical Trial Agreement.

Celularity will ensure that Celularity-sponsored studies are considered for publication in scientific literature in a peer-reviewed journal, irrespective of the results. This applies to results of all Phase 3 clinical studies, and any other study results of significant medical importance, at a minimum. This also includes results relating to investigational medicines whose development programs have been discontinued.

Study results may also be presented at one or more medical congresses and may be used for scientific exchange and teaching purposes. This study and its results may be submitted for inclusion in appropriate health authority study registries, as well as publication on health authority study registry websites, as required by local health authority regulations.

Eligibility for external authorship, as well as selection of first authorship, will be based on several considerations, including, but not limited to, contribution to protocol development, study recruitment, data quality, participation in data analysis, participation in study steering committee (when applicable), and contribution to abstract, presentation and/or publication development.

APPENDIX A. SEQUENTIAL ORGAN FAILURE ASSESSMENT (SOFA) SCORE

SOFA score	1	2	3	4
Respiration ^a				
PaO ₂ /FIO ₂ (mm Hg)	<400	<300	<220	<100
SaO ₂ /FIO ₂	221-301	142-220	67-141	<67
Coagulation				
Platelets x 10 ³ /mm ³	<150	<100	<50	<20
Liver				
Bilirubin (mg/dL)	1.2-1.9	2.0-5.9	6.0-11.9	>12.0
Cardiovascular ^b				
Hypotension	MAP <70	Dopamine ≤5 or dobutamine (any)	Dopamine >5 or norepinephrine ≤0.1	Dopamine >15 or norepinephrine >0.1
Central Nervous System				
Glasgow Coma Score	13-14	10-12	6-9	<6
Renal				
Creatinine (mg/dL) or urine output (mL/d)	1.2-1.9	2.0-3.4	3.5-4.9 or <500	>5.0 or <200
Abbreviations: MAP, mean arterial pressure; SaO ₂ , peripheral arterial oxygen saturation ^a PaO ₂ /FIO ₂ ratio was used preferentially. If not available, the SaO ₂ /FIO ₂ ratio was used ^b vasoactive medications administered for at least 1 hour (dopamine and norepinephrine μmg/kg/min).				

Source: Jones, 2009

APPENDIX B. KARNOFSKY PERFORMANCE STATUS

100	Normal; No complaints; No evidence of disease. Able to work.
90	Able to carry on normal activity, Minor symptoms. Able to work.
80	Normal activity with effort; Some symptoms. Able to work.
70	Cares for self; Unable to carry on normal activity. Independent; not able to work.
60	Disabled; dependent. Requires occasional assistance; cares for most needs.
50	Moderately disabled; dependent. Requires considerable assistance and frequent care.
40	Severely disabled; dependent. Requires special care and assistance.
30	Severely disabled. Hospitalized, death not imminent.
20	Very sick. Active supportive treatment needed.
10	Moribund. Fatal processes are rapidly progressing

Source: [Mor 1984](#)

APPENDIX C. NATIONAL EARLY WARNING SCORE 2 (NEWS2) SCORE

NEWS key		FULL NAME	
0	1	2	3
		DATE OF BIRTH	
		DATE OF ADMISSION	
DATE		DATE	
TIME		TIME	
A+B Respirations Breaths/min	≥25		3
	21–24		2
	18–20		
	15–17		
	12–14		
	9–11		1
≤8		3	
A+B SpO ₂ Scale 1 Oxygen saturation (%)	≥96		
	94–95		1
	92–93		2
	≤91		3
SpO₂ Scale 2† Oxygen saturation (%) Use Scale 2 if target range is 88–92%, eg in hypercapnic respiratory failure †ONLY use Scale 2 under the direction of a qualified clinician	≥97 on O ₂		3
	95–96 on O ₂		2
	93–94 on O ₂		1
	≥93 on air		
	88–92		
	86–87		1
	84–85		2
	≤83%		3
Air or oxygen?	A=Air		
	O ₂ L/min		2
	Device		
C Blood pressure mmHg Score uses systolic BP only	≥220		3
	201–219		
	181–200		
	161–180		
	141–160		
	121–140		
	111–120		
	101–110		1
	91–100		2
	81–90		
	71–80		
	61–70		
	51–60		3
≤50			

Sample NEWS2 Score calculation: Page 1 of 2

Source: [Royal College of Physicians 2017](#)

National Early Warning Score 2 (NEWS2) © Royal College of Physicians 2017

Confidential and Proprietary

APPENDIX D. ORDINAL SCALE FOR CLINICAL IMPROVEMENT

Patient State	Descriptor	Score
Uninfected	No clinical or virological evidence of infection	0
Ambulatory	No limitation of activities	1
	Limitation of activities	2
Hospitalized Mild disease	Hospitalized, no oxygen therapy	3
	Oxygen by mask or nasal prongs	4
Hospitalized Severe Disease	Non-invasive ventilation or high-flow oxygen	5
	Intubation and mechanical ventilation	6
	Ventilation + additional organ support – pressors, RRT, ECMO	7
Dead	Death	8

Source: [World Health Organization \(WHO\) R&D Blueprint novel Coronavirus; COVID-19 Therapeutic Trial Synopsis, 2020.](#)

Appendix 16.1.9 Documentation of Statistical Methods

- Statistical Analysis Plan, Version 1.0, dated 16 September 2021

**A PHASE I/II STUDY OF HUMAN PLACENTAL HEMATOPOIETIC STEM CELL DERIVED NATURAL
KILLER CELLS (CYNK-001) FOR THE TREATMENT OF ADULTS WITH COVID-19**

Protocol Number: CYNK-001-COVID-19

[figure not shown]
IND Number: 019650

Date of Protocol Version : 04 February 2021 (Amendment 5.1)

Sponsor Name: Celularity Inc.

Statistical Analysis Plan, Version 1.0

September 16, 2021

STUDY SUMMARY

Title:	A Phase I/II study of human placental hematopoietic stem cell derived natural killer cells (CYNK-001) for the treatment of adults with coronavirus disease (COVID-19)
Design:	A two-stage study, single arm at phase I and open-label two-arm 1:1 randomization with control at phase II, to investigate the safety, tolerability and efficacy of CYNK-001 on subjects with COVID-19
Investigational Drug:	CYNK-001
Reference Treatment:	Current standard of care for COVID-19 subjects
Population:	86 COVID-19 subjects in total (14 in phase I and 72 in phase II)
Study Duration:	The enrollment is expected for 5 months starting in May, 2020; each subject is expected to receive up to 3 doses in the first week and stay in the study for another 3 weeks. After that, each subject will be followed up to 6 months after randomization day.
Primary Objectives:	Phase I –To evaluate safety, tolerability and efficacy of CYNK-001 Phase II – To evaluate efficacy of CYNK-001
Primary Endpoints:	Phase I – Safety will be assessed by the frequency and severity of adverse events, changes in vital signs, laboratory assessments, Performance Status assessment, and immunological and inflammation assessments. Efficacy will be determined by time to clinical improvement at Day 15 using the Ordinal Scale for Clinical Improvement (OSCI), as defined by the World Health Organization (WHO). Phase II – Efficacy is determined by time to clinical improvement using the OSCI
Secondary Objectives:	Phase II – To determine A) safety and tolerability of CYNK-001 as measured by the frequency and severity of adverse events (AEs) using CTCAE 5.0, and B) overall clinical benefit of receiving CYNK-001 for COVID-19 as measured by rate of clinical improvement by OSCI, time to and rate of clinical improvement by NEWS2 Score, and all-cause mortality rate, time to and rate of clearance of SARS-CoV-2, time to and rate of pulmonary clearance, duration of

hospitalization, supplemental oxygen-free days, proportion of subjects requiring ventilation, SOFA score, and radiologic evaluation score.

Secondary Endpoints: Phase II – A) Safety will be assessed by the frequency and severity of adverse events, changes in vital signs, laboratory assessments, Performance Status assessment, and immunological and inflammation assessments. B) The overall clinical benefit will be evaluated by the rate of clinical improvement by OSCI, time to and rate of clinical improvement by NEWS2 Score, duration of hospitalization, and all-cause mortality rate, time to and rate of clearance of SARS-CoV-2, time to and rate of pulmonary clearance, supplemental oxygen-free days, proportion of subjects requiring ventilation, SOFA score, and radiologic evaluation score.

LIST of ABBREVIATION and SPECIALIST TERM

Abbreviation and Specialist Term	Explanation
AE	Adverse event
AESI	Adverse events of special interest
ARDS	Acute Respiratory Distress Syndrome
CI	Confidence interval
CMV	Cytomegalovirus
COVID-19	coronavirus disease
CT	Computerized tomography
CTCAE	Common Terminology Criteria for Adverse Events
CRS	Cytokine release syndrome
CRP	C-reactive protein
CYNK-001	Investigational product under study; allogeneic off the shelf cell therapy enriched for CD56+/CD3- NK cells expanded from human placental CD34+ cells
DLT	Dose limiting toxicity
DM	Data management
DMC	Data Monitoring Committee
eCRF	Electronic case report form
IV	Intravenous
LOCF	Last observation carry-forward
MedDRA	Medical Dictionary for Regulatory Activities
NEWS2	National Early Warning Score 2
rRT-PCR	Real-time Reverse Transcriptase-Polymerase –Chain Reaction

RFR	Randomization request form
RS	Randomization statistician
RTSM	Randomization and Trial Supply Management System in Clinical One
SAP	Statistical analysis plan
SAE	Serious adverse event
SARS-Cov-2	Severe acute respiratory syndrome coronavirus 2
SOC	Standard of care
SOP	Standard procedure
SpO ₂	Oxygen saturation
SUSAR	Suspected unexpected serious adverse drug reaction
TEAE	Treatment-emergent adverse event

TABLE OF CONTENTS

1.	Introduction	9
2.	Study Objectives	9
2.1	Primary Objective	9
2.2	Secondary Objectives.....	9
2.3	Exploratory Objectives	10
3.	Study Design and Procedures	10
4.	General Analytic Considerations.....	11
	Analysis for Phase I and Phase II will be performed separately.....	11
4.1	Data Sources	11
4.2	Data Sources	11
4.3	Analysis Scope of Data Monitoring Committee (DMC) Meeting and Final Analysis 12	
4.4	Covariate Adjustment	12
4.5	Test Size and Confidence Levels.....	12
4.6	Analysis of safety data	12
4.7	Reporting Timeframe of Measurement for Analysis	13
4.8	General Rules for Summarizing Data	13
5.	Randomization, Allocation Concealment and Blinding	13
5.1	Randomization	13
5.2	Allocation Concealment and Blinding.....	14
5.3	Blinded Data Review	14
6.	Study Size and Power	14
7.	Analysis Populations	15
8.	Data Monitoring Committee (DMC)	15
9.	Subject Disposition and Protocol Violation/Deviation	16
10.	Demographics and Baseline Characteristics	16
11.	Analysis of Study Treatment Exposure	16
12.	Study Day Definition	16
13.	Efficacy Analysis	16
13.1	Phase I Study.....	16
13.2	Phase II Study	17
13.3	Analysis Methods.....	19
13.4	Sensitivity Analysis	22
13.5	Additional Efficacy Analysis.....	22
14.	Safety Analysis	22
14.1	Adverse Events	22
14.2	Laboratory assessment	23
14.3	Vital signs	24
14.4	Physical exams.....	24
14.5	Immunological / Inflammation Assessments.....	24
14.6	Chest X-ray	24
14.7	Infectious Symptom Assessment	24
15.	Changes in Conduct or Planned Analyses from the Protocol	24

16.	Analysis of Concomitant Medication and Concomitant Procedure	25
16.1	Analysis of Prior and Concomitant Medication.....	25
16.2	Analysis of Prior and Concomitant Procedure.....	26
17.	Subgroup Analysis.....	26

1. Introduction

This statistical analysis plan (SAP) expands the analysis plan in *Section 14 Statistics* of the study protocol “A Phase I/II Study of Human Placental Hematopoietic Stem Cell Derived Natural Killer Cells (CYNK-001) for the Treatment of Adults With COVID-19” authored by the sponsor (Celularity Inc) dated February 4, 2021. This is the first version of the SAP and there are no changes to track from a previous approved version. The first approved version of the SAP will be available before the interim analysis of Phase I prior to moving to Phase II. The final approval of SAP from the sponsor and FHI is planned prior to unblinding of the data in Phase II.

The scope of analysis provided in this SAP includes: 1) analysis plan for three scheduled DMC meetings; 2) plan of final analysis for both Phases I and II after trial completion. The analyses in Phase I will assess the tolerability, safety, and efficacy of CYNK-001. The analyses in Phase II will assess safety and efficacy of CYNK-001 in comparison to control (best supportive care).

2. Study Objectives

2.1 Primary Objective

Phase I Study

The primary objectives of the Phase I portion of the study are to evaluate the safety, tolerability, and efficacy of multiple CYNK-001 intravenous (IV) infusions administered with an initial dose of 150×10^6 cells on Day 1 followed by 600×10^6 cells on Days 4 and 7 in subjects with COVID-19.

Phase II Study

The primary objective of the phase II portion is to evaluate the efficacy of CYNK-001 on subjects with COVID-19 by using the Ordinal Scale for Clinical Improvement (OSCI) defined by the World Health Organization (WHO).

2.2 Secondary Objectives

The secondary objectives for the phase II study are:

1. To determine safety and tolerability of CYNK-001 as measured by the frequency and severity of AEs using Common Terminology Criteria for Adverse Events (CTCAE) Version 5.0.
2. To evaluate the overall clinical benefit of receiving CYNK-001 for COVID-19 as measured by rate of clinical improvement by OSCI, time to and rate of clinical improvement by NEWS2 Score,

medical discharge, hospital utilization, all-cause mortality rate, time to and rate of clearance of SARS-CoV-2, time to and rate of pulmonary clearance, supplemental oxygen-free days, proportion of subjects requiring ventilation, SOFA score, and radiologic evaluation score.

2.3 Exploratory Objectives

Exploratory objectives include detection of SARS-CoV-2 via rRT-PCR in various specimen types, cytokine and chemokine measurement, and immune monitoring, alloreactivity measurement.

3. Study Design and Procedures

The study includes two phases with safety and efficacy evaluation between phases to determine the implementation of phase II study.

In the Phase I portion, a total of 14 subjects will be enrolled to assess the safety and efficacy of CYNK-001. To evaluate the safety for potential dose limiting toxicities (DLTs), this phase will enroll 3 subjects initially treated with CYNK-001. If any DLT is observed in the first three subjects, the DMC will be convened for a recommendation. The safety data for these 3 subjects will be evaluated 24 hours after the final dose was provided to the 3rd subject. If deemed safe, the remaining 11 subjects will be enrolled and monitored per the safety stopping rule until Day 15 after the first CYNK-001 infusion.

The starting dose is 150×10^6 cells on Day 1 followed by 600×10^6 cells on Days 4 and 7. The dose limiting toxicities (DLTs) will be evaluated for 28 days following the first dose of the CYNK-001 infusion (Day 1).

MTD is defined as the highest CYNK-001 dose level wherein it was deemed safe per the defined stopping rules or if the DMC recommends stopping the study due to DLTs suspected to be related to CYNK-001. In Phase I, any DLT finding will be forwarded to the DMC for recommendation, review and confirmation as to whether or not the MTD has been exceeded. If the MTD is confirmed by the DMC, no further CYNK-001 administration will occur within that dose level or at any higher dose level.

A de-escalation Dose level -1 will be initiated based on the study stopping rules and DLTs. Dose de-escalation is defined as reducing the frequency of doses by providing doses only on Days 1 and 7 due to potential safety concerns per the DMC recommendation. Once CYNK-001 is deemed safe per the stopping rule and if efficacy is established in at least 2 out of the 14 subjects by Day 15 of the CYNK-001 infusion, it will trigger the initiation of the Phase II of the study. If efficacy has not been demonstrated, the study may stop for futility.

The Phase II portion of the study is a randomized, open-label, multi-site study. 72 Subjects will be randomized to either CYNK-001 (n=36) or Control group (n=36) with best supportive care alone as defined by the hospital by 1:1 ratio, stratified by age (<45 vs. ≥45 years old).

DMC will be convened at midpoint of Phase II (after 18 subjects have received treatment) to evaluate safety and adverse events of interest such as shock, ARDS, and death in the treatment group versus control group. Adverse events of special interest (AESI) will be identified in collaboration with the sponsor and medical monitor.

Each subject is expected to remain in the study for both, treatment period (Day 1 after first infusion to Day 28) and follow-up period (Day 29 to Month 6) with assessment at 3-month and 6-month after infusion.

The study is divided into 3 study periods: Screening Period, Treatment Period, and Follow-up Period, each with associated evaluations and procedures that must be performed at specific timepoints.

4. General Analytic Considerations

Analysis for Phase I and Phase II will be performed separately.

4.1 Data Sources

FHI data management (DM) plans are detailed in a separate study-specific document. In summary, DM will design the eCRF, edit checks and data cleaning. [REDACTED]

The collection and analysis source of lab data, biomarkers and immune monitoring refers to schedule of assessment table in the protocol; and the local lab data will be entered by the site into database. Data will be verified by study monitors and appraised for consistency by FHI 360 DM staff using automated logical checks. Adverse event (AE) will be centrally coded using the Medical Dictionary for Regulatory Activities (MedDRA Version 23.0). No formal adjudication will be performed by FHI 360. SAS datasets (version 9.4 or higher) will be created by FHI 360 DM for use by biostatisticians conducting analysis for DMC meeting purpose and final analyses.

4.2 Missing Data

For time to event data in the efficacy analysis, if the subject withdraws after randomization but before any measurement, the subject will be censored at the randomization date. For subjects who have an

early termination or death, the censoring rule will be described in the corresponding section for each outcome.

For the event rate data in the efficacy analysis, last observation carry-forward (LOCF) will be used if applicable.

The outcomes for safety assessment and assessment additional to efficacy analysis will not be imputed if data is missing.

Please refer to corresponding sections in this SAP for more detail about missing data handling.

Additional rules for imputation of missing data may be determined during blinded review of the data and documented prior to unblinding.

4.3 Analysis Scope of Data Monitoring Committee (DMC) Meeting and Final Analysis

The analysis plan for three scheduled DMC meetings for both phase I and phase II is written in the relevant section independently. The rest of the analysis plan applies to final analysis only after the end of the study, defined as all subjects satisfy the criteria of “End of Study” in the protocol. The analysis for protocol defined exploratory objective will be implemented by Celularity translational team, and thus is not included in the scope of this SAP.

4.4 Covariate Adjustment

For phase I study, no pre-specified set of covariates will be employed to adjust for analysis result.

For phase II study, the primary efficacy endpoint will be adjusted by the age groups (< 45 vs. ≥45 years old). The summary of primary efficacy endpoint by the strata of age, will also be performed in the subgroup analysis. More details will be provided in the corresponding sections of this SAP.

4.5 Test Size and Confidence Levels

Unless otherwise noted, all reported confidence intervals will be computed at the 95% coverage level, and all p-values will be assessed at the two-sided 0.05 significance level, with no further adjustment for multiple testing.

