As a preliminary proof of concept study without relevant data for the new coronavirus disease, 1-sided α of 0.05 will be used in the sample size consideration. With a sample size of 36 for each group (72 in total with 1:1 randomization ratio), a reduction of 50% for the time to event efficacy of CYNK-001 comparing with control can be detected with a power of at least 81% (assuming the time to

clinical improvement is 8 days or earlier for CYNK-001 group, and 16 days or earlier for the control group with the same reduction of 50%) by using Log-rank test. This estimation is based on the study design with a maximum follow up of 28 days for each subject for primary analysis.

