5.3 Blinded Data Review

Prior to scheduled unblinding and final data cleaning, the data may be reviewed in a blinded fashion. Based on analysis needs, the lead statistician will develop specific listings for this review and will document the sponsor or stakeholders' decisions prior to unblinding. [REDACTED]

[REDACTED] Blinded data review may also include clinical evaluation of safety data for reasonableness or to issue clinical queries to the site if needed. Any decisions affecting analysis will be described in internal documentation and the CSR.

6. Study Size and Power

Phase I Study

Fourteen (14) subjects will be treated with CYNK-001 in the Phase I portion. This sample size is determined to be adequate for the evaluation of safety and potential efficacy, based on clinical

judgement for this coronavirus disease and the current treatment status before starting Phase II portion. This number is not driven by hypothesis testing and power calculation.

Phase II Study

The primary efficacy endpoint is time to clinical improvement on the Ordinal Scale for Clinical Improvement (OSCI) defined by the World Health Organization (WHO), at Day 15. As preliminary purpose of proof of concept, without relevant data for the new coronavirus disease, no multiplicity will be adjusted and a 1-sided α of 0.05 will be used for the sample size consideration. With a sample size of 36 for each group (72 in total with 1:1 randomization ratio), a reduction of 50% for the time to event efficacy of CYNK-001 comparing with control can be detected with a power of at least 81% (assuming the time to clinical improvement is 8 days or earlier for CYNK-001 group, and 16 days or earlier for the control group with the same reduction rate of 50%) by using Log-rank test. This estimation is based on the study design with endpoint assessment at 28 days after infusion for each subject.

7. Analysis Populations

- Screened population – include the subjects who are screened.
- Safety Population – include all subjects who receive any amount of CYNK-001 in either phase or who enroll into the control group in phase II. Subjects will be analyzed according to the actual treatment they received for safety analysis.
- ITT Population– the definition of intent-to-treat population applies to phase II only. This population includes all randomized subjects. The subject will be analyzed according to the treatment arm they are randomized to.

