13.3 Analysis Methods

The primary endpoints will be analyzed with hypothesis testing procedures. No formal hypothesis will be carried out for secondary endpoints and the p-values are provided for informative purpose only.

Missing data and censoring will be handled as described below.

- **Primary Efficacy Analysis**

Phase II efficacy data will be analyzed for the ITT population based on randomized treatment group.

The primary efficacy endpoint is the time to clinical improvement on or before Day 28. Kaplan-Meier estimates of the survival curve, estimate of median survival time and its 95% CI will be calculated. Log-rank test will be used to test the difference between treatment groups while adjusting for pre-defined age strata.

Hazard ratio will be estimated via proportional hazard model using treatment as a factor stratified by age group.

Subjects who withdraw after randomization and before any measurements assessed will be censored at randomization date; subjects who terminate from the study before Day 28 without clinical improvement will be censored on the date of the last visit; and subjects who died without clinical improvement by OSCI will be censored on Day 28; subjects without clinical improvement ~~who have no event~~ on or before Day 28 will be censored on Day 28.

- **Secondary Endpoints Analyses**

The analysis will be based on the ITT population unless otherwise specified. Since the purpose of the analysis is for hypothesis generation, no multiplicity adjustment or adjustments for stratification covariates (age and site strata) will be made.

For the endpoints of event rate, including:

- Proportion of subjects who achieved clinical improvements by OSCI

- Proportion of subjects with clearance of SARS-CoV-2 by rRT-PCR
- Proportion of subjects who had pulmonary clearance by LRT specimens where it has previously been found
- Proportion of subjects who need invasive or non-invasive ventilation
- Proportion of subjects who died

The proportions and their two-side 95% CIs will be calculated. Fisher's exact test will be used to test the difference between treatment groups. If the subject has no data after baseline, the subject will be considered as failure in the analysis.

For endpoints of time to event, including:

- Time to clinical improvement measured by NEWS2 Score
- Time to clearance of SARS-CoV-2 by rRT-PCR testing
- Time to disappearance of virus from LRTI specimen
- Time from randomization to medical discharge

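### The stated 81% Phase II power belongs to a one-sided 0.05 test; the two-sided 0.05 test the SAP sets has about 72–75%, and SAP Section 6 also wrongly places the endpoint at Day 15

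*SAP*

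**What the plan says.** **Test level.** SAP Section 4.5 sets the default: "all p-values will be assessed at the two-sided 0.05 significance level, with no further adjustment for multiple testing". It leaves room for exceptions noted elsewhere. SAP 13.3 prescribes an age-stratified log-rank test for the Phase II primary endpoint and gives neither a level nor a sidedness. The same section makes the primary endpoint the only one formally tested; secondary p-values are informative only.

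**Power.** SAP Section 6 states that a "1-sided α of 0.05 will be used for the sample size consideration", and the protocol synopsis says the same ("1-sided α of 0.05 will be used in the sample size consideration"). The design is "With a sample size of 36 for each group (72 in total with 1:1 randomization ratio"), "assuming the time to clinical improvement is 8 days or earlier for CYNK-001 group, and 16 days or earlier for the control group". A halving of the time to improvement "can be detected with a power of at least 81" per cent by log-rank test. Both documents base this on 28 days per subject.

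**Horizon.** The Phase II paragraph of SAP Section 6 describes the primary endpoint as improvement on the OSCI "defined by the World Health Organization (WHO), at Day 15". SAP 13.3 says: "The primary efficacy endpoint is the time to clinical improvement on or before Day 28". SAP 13.1.2, protocol Table 2 (Section 5.4) and protocol Section 6.9 also use Day 28.

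**Status.** SAP Section 15 reports that the sponsor closed the study after 7 patients had been enrolled and dosed in Phase I, and limits the analyses to a Phase I list.

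**The concern.** The power statement is the only quantitative support for 72 subjects in Phase II, and it describes a more lenient test than the one the SAP's general rule assigns to the primary analysis. A reader would take the chance of missing a true halving of the time to improvement as at most 19%. Under the two-sided rule it is about 25–28%.

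The Day 15 phrase is a second inconsistency in the same paragraph. It gives the primary endpoint a horizon that disagrees with the power basis a few lines later and with the endpoint definition and censoring rule. Anyone reusing this plan for a randomised stage would have to guess at both points.

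**Working it through.** **Inputs from the documents:** 36 per arm; 8 versus 16 days; log-rank test; 28 days of follow-up; one-sided 0.05 for sample size (SAP Section 6, protocol synopsis); two-sided 0.05 for analysis (SAP 4.5).

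**Assumptions, not in the documents:** exponential times; 8 and 16 days are medians, so the hazard ratio for improvement is 2; no dropout; no allowance for stratification.

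**1. Expected events by Day 28.** The event probability is 1 − 0.5^(28/median).
- CYNK-001: 1 − 0.5^(28/8) = 0.912
- Control: 1 − 0.5^(28/16) = 0.703
- Events: 36 × (0.912 + 0.703) = 58.1

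**2. Reproduce the stated figure.** Freedman: power = Φ(√d × (HR − 1)/(HR + 1) − z).
- √58.1 × (2 − 1)/(2 + 1) = 7.62/3 = 2.54
- One-sided 0.05: Φ(2.54 − 1.645) = 81.5%, which agrees with the stated figure of at least 81%.

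**3. Change only the sidedness.**
- Two-sided 0.05: Φ(2.54 − 1.96) = 71.9%

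**4. Other methods, same inputs.** Schoenfeld: power = Φ(√d × ln 2 / 2 − z), with 7.62 × 0.693/2 = 2.64.

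| Method | One-sided 0.05 | Two-sided 0.05 |
|---|---|---|
| Freedman | 81.5% | 71.9% |
| Lachin–Foulkes | 81.8% | 72.7% |
| Schoenfeld | 84.1% | 75.2% |
| Simulated log-rank, 5,000 runs | 84.7% | 75.1% |
| Same, times rounded up to whole days | 84.9% | 76.1% |

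The Monte Carlo standard error is about 0.6 points. Two-sided power is about 72–75% by formula, and simulation sits at the upper end.

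**5. Sensitivity: 8 and 16 days as means.** Event probabilities are 1 − e^(−28/8) = 0.970 and 1 − e^(−28/16) = 0.826, giving 64.7 events.
- Freedman, two-sided: Φ(8.04/3 − 1.96) = 76.4%
- Schoenfeld, two-sided: Φ(8.04 × 0.693/2 − 1.96) = 79.6%

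Both remain below 81%. This reading also reproduces the stated figure less well: 85.0% one-sided by Freedman.

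**6. Size needed for 81% at two-sided 0.05, medians reading.** Here (1.96 + 0.878)² = 8.05, and the average event probability is 1.614/2 = 0.807.
- Freedman: 9 × 8.05 = 72.5, so 73 events, and 73/0.807 gives about 91 subjects
- Schoenfeld: 4 × 8.05/0.480 = 67.1, so 68 events, and 68/0.807 gives about 85 subjects

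The plan has 72.

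**The case against.** **The one-sided level in SAP Section 6 may be the exception that Section 4.5 allows.** If so, the primary test is one-sided and the 81% stands. The wording does not favour this: both documents tie the one-sided level to the sample size consideration, and SAP 13.3 does not carry it into the analysis. If one-sided testing was meant, the SAP still needs to say so where the test is defined.

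**The study has closed.** This stands. SAP Section 15 lists only Phase I analyses, so no Phase II log-rank test will be run on these data. The fault lies in the written plan.

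**The size depends on assumptions.** This also stands. The documents do not say that 8 and 16 days are medians or that times are exponential, so a range is needed, not the Freedman figure alone.

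Three stronger readings are tempting and are not supported:

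- *That the planned test has only 59% power.* A 15-day horizon would give 36 × (0.727 + 0.478) = 43.4 events and Φ(6.59/3 − 1.96) = 59.3% at two-sided 0.05. But the power basis, endpoint definition and censoring rule all use Day 28. Day 15 is the Phase I horizon (SAP Study Summary and 13.1.1), so the phrase looks like a carry-over.
- *That a one-sided p-value between 0.025 and 0.05 succeeds under Section 6 and fails under Section 4.5, leaving a choice after the data are seen.* Section 6 sets no success criterion, and there will be no Phase II data from which to choose.
- *That dropout lowers power by a further known amount.* The available text gives no rate. Protocol 6.7 mentions a drop-out assumption without a value, and the Phase II text of protocol 14.8 is absent from the available copy.

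**Conclusion.** The stated power and the stated test level do not belong together. With exponential medians of 8 and 16 days, 36 per arm, 28 days and no dropout, the plan's figure is reproduced only at one-sided 0.05; the two-sided test has about 72–75%, a shortfall of roughly 6 to 9 points against 81%. On the means reading it has about 76–80%, a smaller shortfall. That two-sided power is below the stated figure holds under every method tried; its exact size depends on the assumptions.

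The Day 15 phrase in SAP Section 6 is a separate drafting error that contradicts the operative Day 28 definition. It does not change the power of the planned analysis. Both points concern the correctness of the written Phase II plan and have no effect on the Phase I results to be reported.

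**What to change.** - State the level and sidedness of the Phase II primary log-rank test once, in SAP 13.3, and make Sections 4.5 and 6 agree with it.
- If two-sided 0.05 stays, restate the power as about 72–75% and give the assumptions: exponential times, medians, 28 days and the dropout allowance, if any. Keeping 81% would instead take about 85–91 subjects on the same assumptions.
- If one-sided 0.05 is intended, record it as an explicit exception in Sections 4.5 and 13.3. The 81% can then stand. It should be acknowledged that a positive one-sided result can sit beside a two-sided 95% interval for the hazard ratio that includes 1.
- Delete the Day 15 phrase from the Phase II paragraph of SAP Section 6.

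The cost is SAP wording only, plus a less favourable power figure if the two-sided test is kept. With the study closed, a short correcting note would do; the full change matters if this plan is reused for a randomised stage.
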